2.2.3 Exploratory

- To evaluate a number of pharmacokinetic and pharmacodynamic biomarkers that measure the effect of the combination of palbociclib and dexamethasone including:
 - Plasma levels of palbociclib
 - Western blots of phospho-RB (using antibodies that recognize CDK4/6 phosphorylation sites on RB) and FOXM1 (CDK4/6 substrate which is stabilized by phosphorylation) on lysates from peripheral blood or bone marrow CD19+ cells (obtained by FACS sorting).
 - RNA isolated from CD19+ cells will be used for gene expression profiles (microarray or RNA-Seq) to measure Myb and Bcl-2 levels
 - RNA isolated from CD19+ cells will be used for gene expression profiles (microarray or RNA-Seq) to measure levels of p21, CDK2, and cyclin E as markers of cell cycle activity
 - RNA isolated from CD19+ cells will be used for gene expression profiles (microarray or RNA-Seq) to measure levels of S-Phase and Annexin V/Caspase 3 activation as indicators of proliferation and apoptosis

3 Study Design

This single arm, Phase I, single institution, dose escalation study will follow a traditional 3+3 design (See Section 11).Patients who are receiving treatment with steroids at the time of enrollment must undergo at least a 24 hour washout period prior to their first dose of palbociclib.

Patients will receive a 1-week lead-in (Day -7 to Day -1) of palbociclib alone at the appropriate dose level. This will be followed by induction with 4 weeks of palbociclib in combination with dexamethasone. Patients will receive dexamethasone 20mg daily from days 1-7, 16mg daily from days 8-14, 12mg daily from days 15-21, and 8mg daily from days 22-28. If a patient experiences a DLT as defined in section 6.2.1, the patient will stop the study drugs and come off of the trial. At the completion of induction therapy (Day +28), a bone marrow biopsy will be performed. If the marrow is hypoplastic (<10% cellularity), further treatment will be held (up to 4 weeks from the last day of the induction cycle) to await count recovery. Count recovery will be defined as \geq 10% cellularity in the bone marrow, neutrophils \geq 0.75 x10⁹/L, and a platelet count \geq 75 x 10⁹/L. At the time of count recovery a repeat bone marrow biopsy will be performed. If a CR, CRi, PR, or SD is seen, the patient will move to maintenance therapy.

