Qualified personnel who are familiar with procedures that minimize undue exposure to them and to the environment should undertake the preparation, handling, and safe disposal of chemotherapeutic agents in an appropriate environment.

5.4 **Dose Modifications and Dosing Delays**

Patients who experience a dose limiting toxicity (as defined in section 6.2.1) will stop the study drugs and come off of the trial. The dose cohort level will be de-escalated to 75mg PO daily if dose limiting toxicity occurs in the initial 100mg dose cohort.

Patients who complete the first cycle of maintenance but require treatment to be held up to 4 weeks (after the end of the cycle) to achieve count recovery (as defined below), will have palbociclib resumed with a level -1 dose reduction.

For this study, count recovery is defined as $\geq 10\%$ cellularity in the bone marrow, neutrophils $\geq 0.75 \times 10^{9}$ /L, and a platelet count $\geq 75 \times 10^{9}$ /L.

	Dose*							
Dose Level	Palbociclib (mg)	Dexamethasone (mg)						
Level -1	75	20						
Level 1	100	20						
Level 2	125	20						
Level 3	150	20						

For patients who remain on maintenance after the first cycle, palbociclib dose modifications will be made as follows:

Hematologic toxicity (except lymphopenia unless associated with clinical events [eg opportunistic infection]), according to Common Toxicity Criteria for Adverse Events Version 4.03:

Neutropenia:

Grade 1 or 2: No dosage adjustment required.

Grade 3:

- Day 1 of cycle: Withhold palbociclib therapy and repeat CBC with differential within 1 week. When improved to ≤ grade 2, initiate the next cycle at the same dose. If recovery from grade 3 neutropenia is prolonged (>2 weeks), or for recurrent grade 3 neutropenia on day 1 of subsequent cycles, decrease to next lower dose.
- Grade 3 (ANC 500/mm³ to <1,000/mm³) plus fever ≥38.5°C and/or infection at any time: Withhold palbociclib treatment until resolved to ≤ grade 2. Resume at the same dose.Grade 4 at any time: Withhold palbociclib treatment until resolved to ≤ grade 2. After resolution, resume at next lower dose.

Anemia:

Grade 1, 2, or 3: No dosage adjustment required

Grade 4: Withhold palbociclib treatment until resolved to ≤ grade 2. After resolution, resume at next lower dose.

Thrombocytopenia:

Grade 1 or 2: No dosage adjustment required.

Grade 3:

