	 Grade 3 indirect hyperbilirubinemia that resolves to < grade 2 within 72 hours 								
Renal	Any ≥ Grade 3 toxicity								
Non-	≥ Grade 3, including electrolyte abnormalities, except as noted elsewhere in								
Hematologic	the table								
Exceptions to	Grade 3 alopecia								
DLI criteria	Grade 3 fatigue of < 5 days' duration								
	Grade 3 electrolyte abnormalities that last <72 hours								
	 Infection (including neutropenic fever), unless the investigator 								
	determines that the infection or neutropenic fever resulted from the degree or duration of myelosuppression in the absence of persistent								
	ieureillia								

* CTCAE version 5.0 should be used for grading.

** Optimal therapy for vomiting and diarrhea should be based on institutional guidelines with consideration of the prohibited medications listed in these protocol guidelines.

The DLT evaluation period is defined as 35 days (one week lead-in plus Cycle 1). In order to be considered evaluable, the patient needs to take 80% of the doses in the one week lead-in and Cycle 1 (1 cycle=28 days). The 80% completion can be non-consecutive days of dosing with study drug within the one week lead-in and Cycle 1. Any DLT will be followed until resolution.

If one DLT is recorded, then three additional patients will be enrolled into the present cohort. If no further DLTs occur (1 out of 6 DLTs) then the next patient will be enrolled in the next higher cohort. If 2 out of 6 patients have an observed DLT in any given cohort, 3 additional patients will be treated at one dose level lower, and if no additional DLTs are observed, this will be the maximum tolerated dose. If no DLTs are observed in all three cohorts then the expansion phase dose will be cohort 3 for the expansion phase. Toxicities will be graded according to the National Cancer Institute, Common Toxicity Criteria for Adverse Events version 4.0 (NCI CTCAE v5.0). If multiple toxicities are seen, the presence of DLT will be based on the most severe toxicity experience.

Once three patients have enrolled onto the dose cohort and the DLT evaluation period or the third patient has passed, a meeting will be held with the PI and the TJU Medical Monitor to review the safety information. If it is determined safe to open the next dose cohort, a formal letter from the Medical Monitor will be issued. Please see Appendix D for more information.

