11.2 Analysis Plans

This aim will consist of a Phase I trial of palbociclib to determine the maximum tolerated dose (MTD) of palbociclib when given in combination with dexamethasone. A standard 3+3 dose escalation design will be employed: three dose levels of palbociclib will be explored (100mg, 125mg, 150mg). Patients will be treated in cohorts of size three to six and the dosage will be escalated if the clinical toxicity is acceptable.

Patients who experience a DLT during the evaluation period as defined in section 6.2.1 will stop the study drugs and come off of the trial.

Patients who complete the first cycle of maintenance but require treatment to be held up to 4 weeks to achieve count recovery, will have palbociclib resumed with a level -1 dose reduction. A dose-limiting toxicity (DLT) is defined in the table below:

Toxicity	DLT Criteria*								
Hematology	 Marrow aplasia (defined as <10% cellularity with <10% blasts for ≥ 6 weeks not attributable to disease) 								
	• Grade 4 neutropenia persisting ≥6 weeks from the start of a cycle that								
	is not attributable to the underlying disease								
Cardiac	Any ≥ Grade 3 toxicity								
Gastro-intestinal	Any ≥ Grade 3 toxicity except:								
	 Grade 3 nausea, vomiting**, or diarrhea** not requiring total parenteral nutrition (TPN) or tube-feeding 								
Hepato-biliary	An increase in AST or ALT >3 x ULN and concurrent increase in total								
	bilirubin >2 x ULN (Hy's Law)								
	Any \geq Grade 3 toxicity except:								
	Any Grade 3 or 4 liver abnormalities (AST, ALT, or alkaline								
	phosphatase) that resolve to < grade 2 within 72 hours								
	 Grade 3 hyperbilirubinemia that resolves to < grade 2 within 72 hours One de 2 in dimensional that resolves to < grade 2 within 72 hours 								
	 Grade 3 indirect hyperbilirubinemia that resolves to < grade 2 within 72 hours 								
	nours								
Renal	Any ≥ Grade 3 toxicity								
Non-	≥ Grade 3, except as noted elsewhere in the table								
Hematologic									
Exceptions to	Grade 3 alopecia								
DLT criteria	 Grade 3 fatigue of < 5 days' duration 								
	 Grade 3 electrolyte abnormalities that last <72 hours 								
	 Infection, unless the investigator determines that the infection resulted 								
	from the degree or duration of myelosuppression in the absence of persistent leukemia								

* CTCAE version 5.0 should be used for grading.

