** Optimal therapy for vomiting and diarrhea should be based on institutional guidelines with consideration of the prohibited medications listed in these protocol guidelines.

The design is constructed to reduce the chance of escalating the dose when the probability of DLT is high, and increase the chance of escalating the dose when the probability of DLT is low. The maximum tolerated dose (MTD) is defined as the highest dose level where a DLT occurs in at most one out of six patients treated. The escalation scheme is as follows:

(1) If none of the initial three patients in a cohort experiences a DLT, then a new cohort of three patients will be treated at the next higher dose level.

(2) If one of the three patients in a cohort experiences a DLT, then up to three additional patients will be treated at the same dose. Escalation will continue if only one of six patients experiences DLT.

(3) If two or more patients in a cohort experience DLT, then the MTD will have been exceeded, and no further dose escalation will occur. The previous dose level will be considered the MTD.

(4) If only three patients were treated at a dose level under consideration as the MTD, then up to three additional patients will be accrued. If no more than one of the six patients at that dose level experience a DLT, then that dose level will be confirmed as the MTD. If two or more patients in that cohort experience DLT, then the previous dose level will be studied in the same fashion.

The MTD is defined as the highest dose studied for which the observed incidence of DLT is less than 33%. Frequencies of toxicities will be tabulated according to the NCI Common Toxicity Criteria. Patients will be continued to be followed for one year for evidence of late toxicity.

Table 1.1 below gives the probabilities of dose escalation based on true DLT risk in the 3+3 design.

True DLT rate										
		10%	20%	30%	40%	50%	60%	70%	80%	90%
Probability c escalation	of	0.91	0.71	0.49	0.31	0.17	0.08	0.03	0.01	0.001

All patients treated with at least one dose will be included in the safety analysis.

Response criteria for the study are defined as follows:

Response Criteria Complete Remission (CR) No lymphoblasts in the bone marrow Absolute neutrophil count ≥0.75 x10⁹/L Platelet count ≥75 x 10⁹ /L

Complete Remission with Incomplete Hematologic Recovery (CRi)

<5% lymphoblasts in the bone marrow

Partial Remission (PR)

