11.3 Sample Size Considerations

This traditional 3+3 dose escalation study will include a minimum of 4 and a maximum of 24 participants. The minimum sample size of 4 would be achieved if \geq 2 patients out of the first 3 patients have a DLT at dose levels 1 and -1. The maximum sample size of 18 would be achieved if 6 patients are enrolled at dose levels -1 through 3 (100 mg, 125mg, 150mg, 175mg). The anticipated sample size is 12-18.

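### Section 5.4 steps the 100 mg cohort down to 75 mg on an uncounted DLT, which read literally contradicts the 3+3 rule in Sections 6.2.1 and 11.2

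*Combined protocol and SAP*

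**What the plan says.** Section 5.4 (Dose Modifications and Dosing Delays) contains this cohort rule: "The dose cohort level will be de-escalated to 75mg PO daily if dose limiting toxicity occurs in the initial 100mg dose cohort". No count is attached. The sentence before it cites Section 6.2.1, but only for the definition of a DLT in an individual patient who then leaves the trial.

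Section 6.2.1 (Dose Escalation Procedures) gives a count: "If one DLT is recorded, then three additional patients will be enrolled into the present cohort". It moves up a level if the result is one DLT in six, and down a level at two in six, for any cohort.

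Section 11.2 (Analysis Plans), rule (2), agrees: "If one of the three patients in a cohort experiences a DLT, then up to three additional patients will be treated at the same dose". It continues: "Escalation will continue if only one of six patients experiences DLT". Rule (3) treats two or more DLTs in a cohort as exceeding the maximum tolerated dose (MTD).

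No section exempts the 100 mg starting cohort from these rules. Section 3 refers the reader to Section 11 for the 3+3 design. Table 1.1 in Section 11.2 gives the probability of escalation by true DLT rate under that design.

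**The concern.** Suppose exactly one of the first three patients at 100 mg has a DLT. Section 5.4, taken at its word, makes 75 mg the next dose. Sections 6.2.1 and 11.2 make 100 mg the next dose, for up to three more patients. The documents do not say which section governs.

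The decision feeds the primary endpoint, the MTD. Following Section 5.4 literally would leave 100 mg on evidence that the design treats as insufficient. It could stop the trial from reaching 125 mg when the 3+3 rule would have gone there.

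A reader has some reason to turn to Section 5.4 for this decision. Section 11.2 lists only 100, 125 and 150 mg as the levels to be explored. The dose tables show 75 mg as Level -1, but Section 5.4 has the only sentence that names 75 mg as the place a cohort goes from 100 mg.

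**Working it through.** **Inputs.** The decision rules are those of Sections 5.4, 6.2.1 and 11.2. The printed probabilities are those of Table 1.1. The documents state no expected true DLT rate at 100 mg, so p = 0.10, 0.20 and 0.30 are assumptions. For literal Section 5.4, the step-down is taken to follow any DLT among the first three patients.

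**Step 1: reproduce Table 1.1.** Under 3+3 the dose rises after 0 of 3, or after 1 of 3 followed by 0 of 3:

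E(p) = (1−p)³ + 3p(1−p)² × (1−p)³

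- p = 0.10: 0.729 + 0.243 × 0.729 = 0.906
- p = 0.20: 0.512 + 0.384 × 0.512 = 0.709
- p = 0.30: 0.343 + 0.441 × 0.343 = 0.494

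**Step 2: the same quantity under literal Section 5.4.** Only 0 of 3 allows escalation, so the probability is (1−p)³.

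| True DLT rate | Table 1.1 | 3+3 | Literal 5.4 |
|---|---|---|---|
| 10% | 0.91 | 0.906 | 0.729 |
| 20% | 0.71 | 0.709 | 0.512 |
| 30% | 0.49 | 0.494 | 0.343 |
| 40% | 0.31 | 0.309 | 0.216 |
| 50% | 0.17 | 0.172 | 0.125 |
| 60% | 0.08 | 0.082 | 0.064 |
| 70% | 0.03 | 0.032 | 0.027 |
| 80% | 0.01 | 0.009 | 0.008 |
| 90% | 0.001 | 0.001 | 0.001 |

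All nine printed entries match 3+3 at the printed rounding. Under literal Section 5.4 the first six do not match; the last three cannot tell the two rules apart. Table 1.1 was therefore built on the rule in Sections 6.2.1 and 11.2.

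**Step 3: how often the rules conflict in the first three patients.** With 0 of 3, both escalate. With 2 or 3 of 3, both leave 100 mg downward. They differ only at exactly 1 of 3, which has probability 3p(1−p)²:

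- p = 0.10: 3 × 0.10 × 0.81 = 0.243
- p = 0.20: 3 × 0.20 × 0.64 = 0.384
- p = 0.30: 3 × 0.30 × 0.49 = 0.441

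**Step 4: what follows in those cases.** Under 3+3, the part that would have escalated is 3p(1−p)² × (1−p)³ = 0.177, 0.197 and 0.151. In the rest, 0.243 − 0.177 = 0.066, 0.384 − 0.197 = 0.187 and 0.441 − 0.151 = 0.290, a further DLT appears and 3+3 also steps down. Section 5.4 then only gets there up to three patients sooner.

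**Step 5: probability of leaving 100 mg downward.** Under 3+3 this is 1 − E(p) = 0.094, 0.291 and 0.506. Under literal Section 5.4 it is 1 − (1−p)³ = 0.271, 0.488 and 0.657.

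**The case against.** The best reply is that nobody would run the trial this way. The précis and Sections 3, 6.2.1, 11.2 and 11.3 all name a 3+3 design, Section 3 sends the reader to Section 11, and Section 6.2.1 gives its step-down count for any cohort. On this view Section 5.4 merely names the destination below 100 mg. Once three patients have completed the DLT period, the investigator and the Medical Monitor also review safety, and the Medical Monitor must approve in writing before the next dose cohort opens.

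Most of this stands. Shorthand is the likeliest explanation, and the review makes a wrong action less likely. It does not remove the contradiction: no order of precedence is stated, and the review as described in Section 6.2.1 sets no DLT count for a step-down. That section refers to Appendix D for more detail. The appendix text is not in the material available here, so whether it gives a count is unknown.

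A reader might infer two further points that the documents do not support.

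- **A second conflict later in the trial.** Rule (4) of Section 11.2 covers expanding 100 mg from three to six patients after 125 mg fails: "If no more than one of the six patients at that dose level experience a DLT, then that dose level will be confirmed". One might set Section 5.4 against this too. But Section 5.4 is limited to the initial 100 mg cohort, which need not include patients added later. Section 6.2.1 already disagrees with rule (4) here, because it makes the lower dose the MTD only if the three added patients have no DLT. That mismatch exists without Section 5.4.
- **The minimum sample size of 4 as further proof.** Section 11.3 derives it from "2 patients out of the first 3 patients have a DLT at dose levels 1 and -1" or more. To say that a one-DLT trigger would allow a minimum of 3 requires a cohort to close at the triggering DLT, which Section 5.4 does not say. The same paragraph also gives maxima of both 24 and 18, so it is weak evidence either way.

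**Conclusion.** The point holds as an internal inconsistency in a dose-decision rule. For exactly one DLT in the first three patients at 100 mg, the protocol prescribes two different next doses, and Section 5.4 is the wrongly worded one. It should be fixed before it has to be applied.

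The sizes are conditional on staff following Section 5.4 literally and on assumed true DLT rates of 10%, 20% and 30%. On those terms the conflict arises with probability 0.24, 0.38 and 0.44, and the chance of direct escalation from 100 mg falls by 0.18, 0.20 and 0.15. These are not the expected effect on the trial, because literal use is unlikely.

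Two stronger conclusions would be wrong. This is not a fault in the 3+3 design or in Table 1.1, which is correct as printed. Nor is it an overdosing hazard, since any error sends patients to a lower dose.

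**What to change.** Replace the sentence in Section 5.4 with:

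*If two or more of up to six patients at 100 mg have a DLT, the next cohort is treated at 75 mg (see 6.2.1 and 11.2).*

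This covers both two of three and two of six, keeps 75 mg as the named destination, and ties the step-down to the sections that define the design. Table 1.1 and Sections 6.2.1 and 11.2 need no change for this point. The cost is one sentence in a protocol amendment, with no extra patients or procedures.

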5.5 Study Product

Dexamethasone (Decadron®)

5.6 Study Product Description

Dexamethasone is a synthetic adrenocortical steroid.

5.6.1 Acquisition

Dexamethasone will be billed to patient insurance and handled through the Jefferson outpatient pharmacy.

5.6.2 Formulation, Packaging, and Labeling

Dexamethasone tablets, for oral administration, are supplied in, 0.5 mg and 0.75, mg, 1 mg, 2mg, 4mg and 6 mg tabs. Inactive ingredients are calcium phosphate, lactose, magnesium stearate, and starch. Dexamethasone 0.5 mg also contain D&C Yellow 10 and FD&C Yellow 6. Dexamethasone 0.75 mg also contain FD&C Blue 1.

5.6.3 **Product Storage and Stability**

Store at controlled room temperature 20° to 25°C (68° to 77°F).

5.7 **Dosage, Preparation, and Administration**

The dose of dexamethasone will start at 20mg daily and will taper by 4mg each week over the course of induction. During maintenance, patients will receive 20mg of dexamethasone daily for 7 days. Patients will receive a daily oral dose of dexamethasone.

Dexamethasone will be dispensed from a commercial outpatient pharmacy. It will be dispensed in pill bottle(s) containing a full cycle's amount of dexamethasone. Patients may start a cycle as an outpatient and may self-administer doses at home. Patients will be asked to bring their pill bottle as well as their pill diary to each visit.

5.8 **Dose Modifications and Dosing Delays**

During induction, patients will undergo a planned dexamethasone taper as follows: 20mg of dexamethasone daily from days 1-7, 16mg of dexamethasone daily from days 8-14, 12mg of dexamethasone daily from days 15-21, and 8mg of dexamethasone daily from days 22-28. During maintenance, patients will receive dexamethasone 20mg daily from days 1-7 without a taper.

5.9 **Study Product Accountability**

The IDS at TJU will be responsible for the storage, management, and distribution of the study drug. Patients will be asked to return unused medication at the end of treatment or at the time of withdrawal from the study.

5.10 Assessing Participant Compliance with Study Product Administration

Patients will be given pill diaries and asked to complete it to assess compliance.

5.11 **Concomitant Medications/Treatments**

Patients must not have received any investigational medications within 30 days of study entry unless they have exceeded 5 terminal half-lives of the previous study drug used for treatment.

The following list of medications/treatments will be screened for with potential alteration for the concomitant medication (not steroids), but are not exclusionary.

Aminoglutethimide: Aminoglutethimide may diminish adrenal suppression by corticosteroids.

Amphotericin B injection and potassium-depleting agents: When corticosteroids are administered concomitantly with potassium-depleting agents (e.g., amphotericin B, diuretics), patients should be observed closely for development of hypokalemia. In addition, there have been cases reported in which concomitant use of amphotericin B and hydrocortisone was followed by cardiac enlargement and congestive heart failure.

Antibiotics: Macrolide antibiotics have been reported to cause a significant decrease in corticosteroid clearance (see Drug Interactions, Hepatic Enzyme Inducers, Inhibitors and Substrates). NDA 11-664/S-062 Page 7

Anticholinesterases: Concomitant use of anticholinesterase agents and corticosteroids may produce severe weakness in patients with myasthenia gravis. If possible, anticholinesterase agents should be withdrawn at least 24 hours before initiating corticosteroid therapy.

Anticoagulants, oral: Co-administration of corticosteroids and warfarin usually results in inhibition of response to warfarin, although there have been some conflicting reports. Therefore, coagulation indices should be monitored frequently to maintain the desired anticoagulant effect.

Antidiabetics: Because corticosteroids may increase blood glucose concentrations, dosage adjustments of antidiabetic agents may be required.

Antitubercular drugs: Serum concentrations of isoniazid may be decreased.

Cholestyramine: Cholestyramine may increase the clearance of corticosteroids.

Cyclosporine: Increased activity of both cyclosporine and corticosteroids may occur when the two are used concurrently. Convulsions have been reported with this concurrent use.

Dexamethasone suppression test (DST): False-negative results in the dexamethasone suppression test (DST) in patients being treated with indomethacin have been reported. Thus, results of the DST should be interpreted with caution in these patients.

Digitalis glycosides: Patients on digitalis glycosides may be at increased risk of arrhythmias due to hypokalemia.

Ephedrine: Ephedrine may enhance the metabolic clearance of corticosteroids, resulting in decreased blood levels and lessened physiologic activity, thus requiring an increase in corticosteroid dosage.

Estrogens, including oral contraceptives: Estrogens may decrease the hepatic metabolism of certain corticosteroids, thereby increasing their effect.

Hepatic Enzyme Inducers, Inhibitors and Substrates: Drugs which induce cytochrome P450 3A4 (CYP 3A4) enzyme activity (e.g., barbiturates, phenytoin, carbamazepine, rifampin) may enhance the metabolism of corticosteroids and require that the dosage of the corticosteroid be increased. Drugs which inhibit CYP 3A4 (e.g., ketoconazole, macrolide antibiotics such as erythromycin) have the potential to result in increased plasma concentrations of corticosteroids. Dexamethasone is a moderate inducer of CYP 3A4. Co-administration with other drugs that are metabolized by CYP 3A4 (e.g., indinavir, erythromycin) may increase their clearance, resulting in decreased plasma concentration.

Ketoconazole: Ketoconazole has been reported to decrease the metabolism of certain corticosteroids by up to 60%, leading to increased risk of corticosteroid side effects. In addition, ketoconazole alone can inhibit adrenal corticosteroid synthesis and may cause adrenal insufficiency during corticosteroid withdrawal.

Nonsteroidal anti-inflammatory agents (NSAIDS): Concomitant use of aspirin (or other nonsteroidal anti-inflammatory agents) and corticosteroids increases the risk of gastrointestinal side effects. Aspirin should be used cautiously in conjunction with corticosteroids in hypoprothrombinemia. The clearance of salicylates may be increased with concurrent use of corticosteroids.

Phenytoin: In post-marketing experience, there have been reports of both increases and decreases in phenytoin levels with dexamethasone co-administration, leading to alterations in seizure control.

Skin tests: Corticosteroids may suppress reactions to skin tests.

Thalidomide: Co-administration with thalidomide should be employed cautiously, as toxic epidermal necrolysis has been reported with concomitant use.

6 Study Schedule

